3.1.1.2. Systemic Events

During the reactogenicity e-diary reporting period, participants will be asked to assess vomiting, diarrhea, headache, fatigue, chills, new or worsened muscle pain, and new or worsened joint pain and to record the symptoms in the reactogenicity e-diary. The symptoms will be assessed by the participant as absent, mild, moderate, or severe according to the grading scale in Table 5.

Table 5. Systemic Event Grading Scale

	Mild (Grade 1)	Moderate (Grade 2)	Severe (Grade 3)	Potentially Life-Threatening (Grade 4)
Vomiting	1-2 times in 24 hours.	>2 times in 24 hours.	Requires IV hydration.	Emergency room visit or hospitalization for hypotensive shock.
Diarrhea	2 to 3 loose stools in 24 hours.	4 to 5 loose stools in 24 hours.	6 or more loose stools in 24 hours.	Emergency room visit or hospitalization for severe diarrhea.
Headache	Does not interfere with activity.	Some interference with activity.	Prevents daily routine activity.	Emergency room visit or hospitalization for severe headache.
Fatigue/tiredness	Does not interfere with activity.	Some interference with activity.	Prevents daily routine activity.	Emergency room visit or hospitalization for severe fatigue.
Chills	Does not interfere with activity.	Some interference with activity.	Prevents daily routine activity.	Emergency room visit or hospitalization for severe chills.
New or worsened muscle pain	Does not interfere with activity.	Some interference with activity.	Prevents daily routine activity.	Emergency room visit or hospitalization for severe new or worsened muscle pain.

Table 5.	Systemic Ev	vent Grading S	scale
	~,, > = = = = =	· • • • • • • • • • • • • • • • • • • •	

	Mild (Grade 1)	Moderate (Grade 2)	Severe (Grade 3)	Potentially Life-Threatening (Grade 4)
New or worsened joint pain	Does not interfere with activity.	Some interference with activity.	Prevents daily routine activity.	Emergency room visit or hospitalization for severe new or worsened joint pain.

Abbreviation: IV = intravenous.

The derivations for systemic events will be handled similarly to the way local reactions are handled for presence of event, severity level, duration, and onset day. The variables associated with the systemic events will be computed similarly to the way local reactions are computed (see Section 3.1.1.1).

3.1.1.3. Fever

Oral temperature will be collected in the reactogenicity e-diary in the evening daily during the reactogenicity e-diary reporting period. It will also be collected at any time during the reactogenicity e-diary data collection periods when fever is suspected. Fever is defined as an oral temperature $\geq 38.0^{\circ}$ C ($\geq 100.4^{\circ}$ F). The highest temperature for each day will be recorded in the reactogenicity e-diary. Temperature will be measured and recorded to 1 decimal place.

Temperatures recorded in degrees Fahrenheit will be programmatically converted to degrees Celsius for reporting. Temperatures <35.0°C and >42.0°C will be excluded from the analysis. Fever will be grouped into ranges for the analysis according to Table 6.

Table 6. Scale for Fever

\geq 38.0°C to 38.4°C (100.4°F to 101.1°F)
>38.4°C to 38.9°C (101.2°F to 102.0°F)
>38.9°C to 40.0°C (102.1°F to 104.0°F)
>40.0°C (>104.0°F)

Note: Fever is defined as an oral temperature ≥ 38.0 °C (≥ 100.4 °F).

3.1.1.4. Use of Antipyretic Medication

The use of antipyretic medication to treat symptoms associated with study intervention administration will be recorded in the reactogenicity e-diary daily during the reporting period (Day 1 through Day 7).

For the use of antipyretic medication from Day 1 through Day 7 after each dose, the following endpoints and variables will be derived for analysis following the same rules as for local reactions (see Section 3.1.1.1), where applicable:

- Presence (yes or no) of use of antipyretic medication on each day (Day 1-7).
- Presence (yes or no) of use of antipyretic medication on any day (Day 1-7).
- Duration (first to last day reported) of use of antipyretic medication.
- Onset day of use of antipyretic medication.

The use of antipyretic medication will be summarized and included in the systemic event summary tables but will not be considered a systemic event.

3.1.1.5. Adverse Events

The time period for actively eliciting and collecting AEs and SAEs, "the active collection period," for each participant begins from the time the participant provides informed consent, which is obtained before the participant's participation in the study (ie, before undergoing any study-related procedure and/or receiving study intervention), through and including Visit 206 (4-week follow-up visit) for Substudy B. Additionally, for Substudy B, any AEs occurring up to 48 hours after the blood draws at Visits 206 and 207 must be recorded on the CRF.

Acute reactions within the first 30 minutes after each vaccination will be assessed and documented in the AE CRF. Such acute reactions, if any, are defined as immediate AEs.

SAEs will be collected from the time the participant provides informed consent to approximately 6 months after the participant's last study vaccination (Visit 208 for Substudy B).

Adverse events of special interest include:

- A confirmed diagnosis of influenza;
- A confirmed diagnosis of myocarditis or pericarditis.

3.1.1.6. Chemistry Laboratory Parameters

Troponin I laboratory parameters will be collected. The primary endpoints include abnormal troponin values 2 days after the last vaccination.

The troponin I tests will be performed at screening and Visits 201 (Day 1) and 204 (2 to 4 days after the last vaccination).

The investigator must review the laboratory report, document this review, and record any clinically relevant changes occurring during the study in the AE section of the CRF.

3.1.1.7. Electrocardiograms

An ECG abnormality is defined as any new abnormality that, as judged by a cardiologist, is consistent with probable or possible myocarditis or pericarditis, including but not limited to the following:

- Sustained atrial or ventricular arrhythmias
- Second-degree Mobitz Type II or worse atrioventricular block, new bundle branch block
- Diffuse ST-segment elevation or PR-segment inversion, compatible with pericarditis

[figure not shown]
3.2. Secondary Endpoints

3.2.1. Immunogenicity Endpoints

In participants complying with the key protocol criteria (evaluable participants), the endpoints include:

HAI titers for each strain targeted by the study vaccine.

3.3. Tertiary/Exploratory Endpoints

3.4. Baseline Variables

Measurements or samples collected prior to vaccination are considered the baseline data for the assessments.

3.4.1. Demographics, Medical History, and Physical Examination

The demographic variables are age at Vaccination 1 (in years), sex (male or female), race (Black or African American, American Indian, or Alaska Native, Asian, Native Hawaiian or other Pacific Islander, White), and ethnicity (Hispanic/Latino[a] or of Spanish origin, non-Hispanic/non-Latino[a] or of Spanish origin). In cases where more than 1 category is selected for race, the participant would be counted under the category "multiracial" for analysis.

Age (in years) will be derived based on the participant's birthday and the date the participant receives Vaccination 1. For example, if the vaccination day is 1 day before the participant's 66th birthday, the participant is considered to be 65 years old. For participants who were randomized but not vaccinated, the randomization date will be used in place of the date of vaccination for the age calculation. If the randomization date is also missing, then the informed consent date will be used for the age calculation.

Medical history will be obtained from all participants at their screening visit to establish a baseline. Significant medical history and observations from any physical examination, if performed, will be documented in the CRF. Medical history will be categorized according to MedDRA.

A physical examination will be performed at the screening visit but is not mandated for Vaccination 1. Physical examination findings collected during the study will be considered source data and will not be required to be reported, unless otherwise noted.

3.4.2. E-Diary Completion

For all participants, an e-diary will be considered transmitted if any data for local reactions, systemic events, or use of antipyretic medication are present for any day. If all data are missing for all items on the e-diary for all 7 days after vaccination, then the e-diary will be considered not transmitted. An e-diary will be considered completed if all expected data for all 7 days are available (ie, not missing). Otherwise, the e-diary will be considered incomplete. For any given day, an e-diary will be considered complete if all expected data are available.

3.4.3. Prior/Concomitant Vaccines and Concomitant Medications

Receipt of the following vaccines and medications during the time periods listed below may exclude a participant from the per-protocol analysis from that point onward and may require vaccinations to be discontinued in that participant; however, it is anticipated that the participant would not be withdrawn from the study. Medications should not be withheld if required for a participant's medical care.

• Unless considered medically necessary, no vaccines other than study intervention should be administered within 28 days before and 28 days after each study vaccination.

- Receipt of any mRNA-platform SARS-CoV-2 vaccine within 28 days before and 28 days after any study vaccination that contains modRNA.
- Receipt of any other (nonstudy) seasonal influenza vaccine is prohibited from enrollment through Visit 207 (8-week follow-up visit).
- Receipt of chronic systemic treatment with known immunosuppressant medications, or radiotherapy, within 60 days before enrollment through conclusion of the study is prohibited.
- Receipt of systemic corticosteroids (≥20 mg/day of prednisone or equivalent) for ≥14 days is prohibited from 28 days prior to enrollment through 28 days after administration of the last study intervention.
- Receipt of blood/plasma products or immunoglobulins within 60 days before enrollment through conclusion of the study is prohibited.

Prophylactic antipyretics and other pain medication to prevent symptoms associated with study intervention administration are not permitted. However, if a participant is taking a medication for another condition, even if it may have antipyretic or pain-relieving properties, it should not be withheld prior to study vaccination.

3.5. Safety Endpoints

Local reaction, systemic event, AE, and SAE assessments, abnormal troponin I laboratory tests, and assessment of ECG abnormalities are described above in the Primary Safety Endpoints section (Section 3.1.1).

4. ANALYSIS SETS (POPULATIONS FOR ANALYSIS)

Data for all participants will be assessed to determine if participants meet the criteria for inclusion in each analysis population prior to unblinding and releasing the database, and classifications will be documented per standard operating procedures. The populations are defined below:

Population	Description	
Enrolled	All participants who sign the ICD.	
Randomly assigned to study intervention	All participants who are assigned a randomization number in the IWR system.	
Evaluable immunogenicity	 All participants who: Are eligible (have signed informed consent and met all inclusion/exclusion criteria); Receive the vaccines according to the group to which they were randomized (ie, 1-visit or 2-visit schedules); 	

Population	Description	
	 Have blood drawn for assay testing within the specified time frame (26-35 days) after the last vaccination (1-visit or 2-visit schedules); Have at least 1 valid and determinate assay result at the 4-week follow-up visit (26-35 days) following the last vaccination (1-visit or 2-visit schedules); Have no major protocol violations. 	
mITT	All randomized participants who:	
	• Receive the study intervention(s) (1-visit or 2-visit schedules);	
	• Have at least 1 valid and determinate assay result after the last vaccination (1-visit or 2-visit schedules).	
	The immunogenicity results based on the mITT population will be summarized for immunogenicity endpoints if there is a $\geq 10\%$ difference between the mITT population and the evaluable immunogenicity population.	
Vaccination 1 safety	All participants who received Vaccination 1 from 2-visit schedule.	
Vaccination 2 safety	All participants who received Vaccination 2 from 2-visit schedule.	
Safety	All participants who received the study intervention.	

The major protocol violations will be determined by the medical monitor. A major protocol violation is a protocol violation that, in the opinion of the sponsor's clinician, would materially affect assessment of immunogenicity, eg, participant receipt of a prohibited vaccine or medication that might affect immune response or a medication error with suspected decrease in potency of the vaccine. The sponsor's clinician will identify those participants with major protocol violations that result in exclusion from analysis populations before any unblinded analysis is carried out.

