9.2. Analysis Sets

For purposes of analysis for the study, the following analysis sets are defined:

Population	Description
Enrolled	All participants who sign the ICD.
Randomly assigned to study intervention	All participants who are assigned a randomization number in the IWR system.
Vaccination 1 evaluable	For Substudy A only. All participants who are eligible, receive the study intervention (Vaccination 1) to which they were randomized, have blood drawn for assay testing within specified time frames after Vaccination 1, have at least 1 valid and determinate assay result at the 4-week post–Vaccination 1 visit, and have no major protocol violations before Vaccination 2.
Vaccination 2 evaluable	All participants who are eligible; receive the first study intervention(s) (Vaccination 1) (1 vaccination, or 2 different vaccinations administrated in the left and right arms) to which they were randomized, and the second study vaccination (Vaccination 2) if they received only 1 vaccination before; have blood drawn for assay testing within specified time frames after Vaccination 2 and have at least 1 valid and determinate assay result at the 4-week post-Vaccination 2 visit, or have blood drawn for assay testing within specified time frames after Vaccination 1 (for participants with 2 vaccinations administrated) and have at least 1 valid and determinate assay result at the 4-week post-Vaccination 1 visit; and have no major protocol violations.
Vaccination 1 mITT	For Substudy A only. All randomized participants who receive the study intervention (Vaccination 1) and have at least 1 valid and determinate assay result after Vaccination 1 but before Vaccination 2.
Vaccination 2 mITT	All randomized participants who receive the study intervention(s) (Vaccination 1 and Vaccination 2; or Vaccination 1 only [2 vaccinations administrated in the left and right arms]) and have at least 1 valid and determinate assay result after Vaccination 2, or have at least 1 valid and determinate assay result after Vaccination 1 (for participants with 2 vaccinations administrated).
Safety	All participants who receive the study intervention.

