5. GENERAL METHODOLOGY AND CONVENTIONS

CIs for all endpoints in the statistical analysis will be presented as 2-sided at the 95% level unless specified otherwise.

The safety analyses are based on the safety populations. Participants will be summarized by vaccine group according to the study interventions they actually received. Completely missing reactogenicity e-diary data will not be imputed; missing AE dates will be handled according to the Pfizer safety rules.

For all the immunogenicity endpoints, the analysis will be based on the evaluable immunogenicity population.

An additional analysis may be performed based on the mITT population if there is a large enough difference in sample size between the mITT population and the evaluable immunogenicity population. Participants will be summarized according to the vaccine group to which they were randomized. Missing serology data will not be imputed.

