6.2. Secondary Endpoints

- 6.2.1. HAI Titers for Each Strain Targeted by the Study Vaccine
- 6.2.1.1. Participants From 65 Through 85 Years of Age
- 6.2.1.1.1 The Analyses in Sections 6.2.1.1.1 to 6.2.1.1.4 are for Participants From 65 Through 85 Years of Age HAI GMTs at Each Scheduled Visit

6.2.1.1.1.1. Main Analysis

- Estimand: HAI GMTs before Vaccination 1, prior to Vaccination 2 (Day 21, if applicable), and at 1, 4, and 8 weeks after the last vaccination.
- Estimand strategy: Hypothetical strategies (Section 2.2.2).
- Analysis set: Evaluable immunogenicity population (Section 4).
- Analysis time points: Day 1 before Vaccination 1, prior to Vaccination 2 (Day 21, if applicable), and at 1, 4, and 8 weeks after the last vaccination.
- Analysis methodology: Descriptive summary statistics.
- Intercurrent events and missing data: Missing immunogenicity results will not be imputed, as MCAR is assumed. For participants who discontinue or have major protocol violations, all postdiscontinuation or postviolation observations will be censored.
- Reporting results: HAI GMTs (Section 5.2.2.1) and associated 2-sided 95% CIs will be provided by vaccine group and strain(s) before Vaccination 1, prior to Vaccination 2 (Day 21, if applicable), and at 1, 4, and 8 weeks after the last vaccination.

Figures:

• Empirical RCDCs (Section 5.2.2.4) will be provided for HAI GMTs by vaccine group and strain(s) before Vaccination 1, prior to Vaccination 2 (Day 21, if applicable), and at 1, 4, and 8 weeks after the last vaccination.

• HAI GMTs and associated 95% CIs will be plotted by vaccine group and strain(s) before Vaccination 1, prior to Vaccination 2 (Day 21, if applicable), and at 1, 4, and 8 weeks after the last vaccination.

6.2.1.1.2. HAI Geometric Mean Fold Rises After Receipt of Vaccination 1

6.2.1.1.2.1. Main Analysis

- Estimand: HAI GMFRs from before Vaccination 1 to prior to Vaccination 2 (Day 21, if applicable) and to 1, 4, and 8 weeks after receipt of the last vaccination.
- Estimand strategy: Hypothetical strategies (Section 2.2.2).
- Analysis set: Evaluable immunogenicity population (Section 4).
- Analysis time points: Day 1 before Vaccination 1 (baseline for calculation) to prior to Vaccination 2 (Day 21, if applicable) and to 1, 4, and 8 weeks after receipt of the last vaccination.
- Analysis methodology: Descriptive summary statistics.

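### In Substudy B's 2-visit groups, Day 21 HAI summaries drop valid post-dose-1 titers because of events that happen after the sample is drawn

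*SAP*

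**What the plan says.** Protocol 10.10.3 and SAP 2.2 make Day 21 a secondary time point for HAI GMT, GMFR, seroconversion and titer of at least 1:40 in adults 65 to 85. For GMTs, SAP 6.2 gives the time points as "Day 1 before Vaccination 1, prior to Vaccination 2 (Day 21, if applicable), and at 1, 4, and 8 weeks after the last vaccination".

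One population serves every time point. SAP 5 states: "For all the immunogenicity endpoints, the analysis will be based on the evaluable immunogenicity population". Each main analysis in SAP 6.2 repeats it: "Analysis set: Evaluable immunogenicity population (Section 4)".

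SAP 4 defines that population by conditions that include:
- "Receive the vaccines according to the group to which they were randomized (ie, 1-visit or 2-visit schedules)"
- "Have at least 1 valid and determinate assay result at the 4-week follow-up visit (26-35 days) following the last vaccination"
- no major protocol violations, with no time limit attached.

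The mITT set in SAP 4 drops the 4-week and no-violation conditions but still asks participants to "Have at least 1 valid and determinate assay result after the last vaccination (1-visit or 2-visit schedules)". It is summarized if it differs from the evaluable set by at least 10%.

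Protocol 9.2 has a dose-1 immunogenicity set, but its definition opens: "For Substudy A only. All participants who are eligible, receive the study intervention (Vaccination 1) to which they were randomized". For Substudy B, SAP 4 has a separate Vaccination 1 set for safety and none for immunogenicity.

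**The concern.** In a 2-visit group the Day 21 titer reflects Vaccination 1 alone. Nothing that happens afterwards can change it, yet later events decide whether it is counted. Those events are whether Vaccination 2 is given, whether a sample 26 to 35 days after it is valid, and whether a major violation occurs at any point.

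Later loss need not be unrelated to dose 1. A related Grade 4 reaction ends further vaccination (Protocol 8.2.3.2, 8.2.3.3), eligibility is rechecked at Visit 203 (10.10.8.8.4), and a stopping rule can pause administration (10.10.8.6). SAP 6.2 nevertheless assumes results are missing completely at random. Participants who do not go on to Vaccination 2 stay in the study for immunogenicity evaluation (Protocol 7.1, 10.10.8.8.4), so the plan collects titers that its main analysis then leaves out.

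At stake is a descriptive Day 21 result that leans toward people who tolerated dose 1 and completed follow-up. There is also a practical risk: the SAP's own rules point to two different Day 21 denominators.

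**Working it through.** The point rests on no figure stated in the plan. The group sizes used below do reproduce: 11 × 15 = 165 in initial enrollment, 13 × 120 = 1560 in expanded enrollment, and 165 + 1560 = 1725. Protocol Table 6 shows four initial 2-visit groups (Groups 1 to 4), so 4 × 15 = 60 initial participants are affected. Groups of 120 matter only if a 2-visit schedule is expanded or the QIV-then-placebo control (Group 12) is opened.

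**1. The SAP's rules side by side**
- SAP 4 removes the whole participant if Vaccination 2, the valid 4-week result or freedom from major violation fails.
- SAP 6.2 censors only observations made after discontinuation or violation. An earlier Day 21 titer would stay.
- SAP 3.4.3 says a prohibited vaccine or medication may exclude a participant from the per-protocol analysis only from the time of that event. Again the Day 21 titer would stay.
- SAP 2.2.2 takes its blood-draw windows from Section 4, which gives only 26-35 days. No window exists for judging a Day 21 draw.

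**2. Who loses a Day 21 titer**
The Day 21 blood is drawn at Visit 203, 19 to 23 days after Visit 201 and before Vaccination 2.

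| Participant | Day 21 titer exists | Evaluable | mITT |
|---|---|---|---|
| Withdraws before Visit 203 | no | no | no |
| Bled at Visit 203, not given Vaccination 2 | yes | no | no (protocol wording) |
| Both doses, 4-week result missing, valid 1- or 8-week result | yes | no | yes |
| Both doses, major violation after Day 21, valid result after the last dose | yes | no | yes |

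The protocol's Vaccination 2 mITT set requires both vaccinations in 2-visit groups. The SAP's mITT wording is looser and could be read to admit the second row; that is not settled.

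**3. The 10% trigger (assumed rates)**
Take n=120, with 10% (12 people) bled at Visit 203 but not dosed, and 5% (6 people) missing the 4-week result but having another later one.
- mITT = 120 − 12 = 108; evaluable = 108 − 6 = 102.
- Difference = 6/108 = 5.6%, so the trigger is not met.
- Day 21 titers left out = 18/120 = 15%.

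**4. Size of the shift (assumed rates)**
Let d be the fraction excluded, and p_E and p_X the seroconversion proportions in those kept and those excluded. Shift = p_E − [(1 − d)p_E + d·p_X] = d(p_E − p_X).
- Low: 0.05 × 0.20 = 1.0 point.
- High: 0.15 × 0.40 = 6.0 points.

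For GMTs, if the excluded have r times the GMT of those kept, the reported GMT is off by a factor r^(−d). With r = 0.5 this is 1.035 at d = 5% and 1.110 at d = 15%. With r = 2 it is 0.966 and 0.901.

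**5. Against precision (Clopper-Pearson, near 50%)**
- n=15, 8/15: 26.6% to 78.7%, half-width 26.1 points; 6/26.1 = 23% of it. One person is 1/15 = 6.7% of the group.
- n=120, 60/120: 40.7% to 59.3%, half-width 9.3 points; 6/9.3 = 65% of it, and 1/9.3 = 11%.

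**The case against.** The strongest reply is that a single evaluable cohort across time points is a deliberate convention. It compares the same people before and after dose 2, and a separate Day 21 set gives up that exact match. Substudy A follows a similar convention: its Vaccination 1 evaluable set also requires a 4-week result, although 1-week endpoints are reported in evaluable participants. This stands as a reason to keep the current-set Day 21 result as a supporting row. It does not explain why SAP 6.2 and 3.4.3 say otherwise.

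Other parts of the reply also stand:
- The mITT analysis rescues some participants, so collected titers are not lost in every case. SAP 7.2 also allows mITT for the IRC review when 4-week data are limited.
- SAP 6.5.2.2 summarizes exclusions with reasons, so the number excluded will be visible even if their Day 21 titers are not.
- Anyone who withdraws before Visit 203 has no Day 21 titer under any set. The loss specific to Vaccination 2 is limited to people bled at that visit and not dosed.
- Substudy B tests no hypothesis, so no error rate is affected.

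A reader might infer that the analysis departs from the estimand the plan states. The documents do not support that: SAP 2.2.2 names the Section 4 evaluable set as the estimand's population, under a hypothetical strategy. The analysis set matches the stated population. The fault is that this population is poorly suited to a pre-Vaccination 2 outcome and conflicts with the censoring rules.

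**Conclusion.** The point holds as a selection problem and an internal inconsistency in a descriptive secondary analysis. Entry to the Day 21 summaries depends on later events, SAP 4 conflicts with SAP 6.2 and 3.4.3, and the mITT fallback covers only part of the gap. Its 10% trigger does not register people bled at Visit 203 but not dosed, if the protocol's mITT wording governs.

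The size is unknown. The 1-6 point range rests on an assumed 5-15% loss and assumed 20-40 point differences, neither of which comes from the documents. It would be minor beside the uncertainty in a group of 15, and a noticeable share of the interval in a group of 120. If those lost respond like those kept, there is no bias, only a small loss of precision.

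A reader might also infer that Substudy A's definition already solves this and need only be extended. It does not: it requires a 4-week post-Vaccination 1 result, and 2-visit participants receive Vaccination 2 at 19 to 23 days.

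**What to change.** In SAP 4, add a Day 21 (Vaccination 1) evaluable set for Substudy B 2-visit schedules, covering participants who:
- are eligible;
- received Vaccination 1 as randomized;
- had the pre-Vaccination 2 draw within the existing Visit 203 window (19-23 days), with at least 1 valid result;
- had no major violation before that draw.

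Use this set for the Day 21 rows in SAP 2.2.2 and 6.2. Keep the current set for time points after the last vaccination. Reconcile the censoring text in 6.2 with Section 4 so that one rule decides whether an earlier valid titer is kept.

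Do not simply delete the Substudy A restriction in Protocol 9.2. If the protocol is amended, add a separate Substudy B definition. Protocol Section 9 lets the SAP modify the outlined analyses and requires an amendment only for major changes to primary endpoints, so the SAP change can stand alone.

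The cost is one population flag and some wording. The Day 21 denominator may differ slightly from later time points in the same table; a supporting Day 21 row in the current set keeps the same-person comparison.

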2.2.2. Secondary Estimands

For the purposes of the study, the following also applies to the tertiary/exploratory estimands:

• Seroconversion is defined as an HAI titer <1:10 prior to vaccination and ≥1:40 at the time point of interest, or an HAI titer ≥1:10 prior to vaccination with a 4-fold rise at the time point of interest.

The secondary estimands for the secondary objective will use the hypothetical strategies from the EMA ICH E9 (R1) addendum¹ and estimate the immune response.

2.2.2.1. HAI Titers for Each Strain Targeted by the Study Vaccine for Each Strain 2.2.2.1.1. Participants From 65 Through 85 Years of Age

• HAI GMTs before Vaccination 1, prior to Vaccination 2 (Day 21, if applicable), and at 1, 4, and 8 weeks after the last vaccination.

This estimand includes the following attributes:

- Treatment: 1-Visit schedules or 2-visit schedules with modRNA, licensed QIV, and/or placebo or their combinations as listed in Table 2.
- Population: Evaluable immunogenicity population as defined in Section 4.
- Variable: HAI GMTs on Day 1 prior to Vaccination 1, prior to Vaccination 2 (Day 21, if applicable), and at 1, 4, and 8 weeks after the last vaccination.
- Intercurrent event(s): For participants who discontinue, have major protocol violations, and/or results obtained from out-of-window blood draws. The windows of blood draws, as mentioned throughout the SAP, refer to the assay windows defined in Section 4 in this SAP.
- Population-level summary: HAI GMTs and associated 2-sided 95% CI for each strain from before Vaccination 1, prior to Vaccination 2 (Day 21, if applicable), and at 1, 4, and 8 weeks after receipt of Vaccination 2.
- HAI GMFRs from before Vaccination 1 to prior to Vaccination 2 (Day 21, if applicable) and to 1, 4, and 8 weeks after receipt of the last vaccination.

- Treatment: 1-Visit schedules or 2-visit schedules with modRNA, licensed QIV, and/or placebo or their combinations as listed in Table 2.
- Population: Evaluable immunogenicity population as defined in Section 4.
- Variable: GMFRs from before Vaccination 1 to prior to Vaccination 2 (Day 21, if applicable) and to 1, 4, and 8 weeks after receipt of the last vaccination.
- Intercurrent event(s): For participants who discontinue, have major protocol violations, and/or results obtained from out-of-window blood draws.

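### SAP 4 removes a major violator altogether while SAP 6.2 censors only later samples, and the secondary all-strains composite leaves out Group 9

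*SAP*

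**What the plan says.** **Violators.** SAP 4 requires that evaluable participants "Have no major protocol violations". The protocol 9.2 set that applies to Substudy B (Vaccination 2 evaluable) has the same unlimited condition. SAP 4 adds that the sponsor's clinician will "identify those participants with major protocol violations that result in exclusion from analysis populations before any unblinded analysis is carried out". SAP 6.2 runs each secondary analysis on this set and states that for participants who discontinue or have major violations, "all postdiscontinuation or postviolation observations will be censored". SAP 2.2.2 lists as intercurrent events: "For participants who discontinue, have major protocol violations, and/or results obtained from out-of-window blood draws". SAP 3.4.3 and protocol 6.8.1 say that a prohibited vaccine or medication can remove a participant from the time of receipt forward; that wording is permissive. The Substudy A set in protocol 9.2 (Vaccination 1 evaluable) asks for a valid result at the 4-week "visit, and have no major protocol violations", and then limits that condition to the time before Vaccination 2.

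**All strains.** Protocol 1.1 and 10.10.3, and SAP 2.2, 2.2.2.2.1 and 6.2.2.1, limit the composite to participants with at least one quadrivalent dose (in SAP 6.2.2.1, qIRV or licensed QIV). Protocol 10.10.9.3.3 and SAP 5.2.1.2 do not repeat the limit.

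**mITT back-up.** SAP 4 also requires: "Have at least 1 valid and determinate assay result at the 4-week follow-up visit (26-35 days) following the last vaccination". It says "The immunogenicity results based on the mITT population will be summarized for immunogenicity endpoints" when the two sets differ by at least 10%. SAP 5 says only that such an analysis *may* be done if the sample sizes differ enough. SAP 2.2.2 says the blood-draw windows "refer to the assay windows defined in Section 4 in this SAP", but that section gives only the 4-week window.

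**The concern.** The set definition and the censoring rule cannot both govern a major violator. If SAP 4 is applied first, no violator is left in the set, so the major-violation words in SAP 6.2 and in the SAP 2.2.2 intercurrent events have no one to act on. If SAP 6.2 is meant to work as written, some violators must be in the set. The N of the secondary tables depends on which text the programmer follows.

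The case that matters is a violation after the 4-week draw. Nonstudy influenza vaccine is prohibited up to Visit 207. Substudy B exclusion criterion 12 refers to the 2022-2023 season, so receipt between Visits 206 and 207 is a realistic example, if it is judged major. It cannot affect the baseline, Day 21, 1-week or 4-week titers, yet literal SAP 4 removes them all.

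For Group 9, the stated secondary estimand gives no all-strains composite, although its schedule targets 2 A and 2 B strains. Its each-strain analyses are unaffected.

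**Working it through.** **Plan's own figures.** 11 initial groups × 15 = 165. Then 165 + 13 × 120 = 1725. Both reproduce.

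**Samples per violator.** Inputs are the HAI draws in the Substudy B schedule of activities (protocol 10.10.1): Visits 201, 205, 206 and 207 for 1-visit schedules (4 samples), plus Visit 203 for 2-visit schedules (5 samples).

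| Violation falls between | Schedule | Drawn before it | Kept by literal SAP 4 | Kept by SAP 6.2 wording alone |
|---|---|---|---|---|
| Visits 206 and 207 | 1-visit | 201, 205, 206 | 0 of 4 | 3 of 4 |
| Visits 206 and 207 | 2-visit | 201, 203, 205, 206 | 0 of 5 | 4 of 5 |
| Visits 205 and 206 | 1-visit | 201, 205 | 0 of 4 | 2 of 4 |
| Visits 205 and 206 | 2-visit | 201, 203, 205 | 0 of 5 | 3 of 5 |

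Over four strains, the first two rows are 3 × 4 = 12 and 4 × 4 = 16 titers per violator.

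**Groups without a quadrivalent dose.** From protocol Table 6, Groups 1, 7, 10, 11, 13 and 14 receive qIRV (6 groups). Groups 2, 3, 4, 5, 6, 8 and 12 receive licensed QIV (7 groups). That makes 13 of 14. Group 9 alone receives neither; its right deltoid gets bIRV 2 × B and its left deltoid bIRV 2 × A. In initial enrollment Group 9 is 15 of 165 participants (15/165 = 9.1%), and one of five groups given 2 A and 2 B strains as IRV only (1, 7, 9, 10, 11).

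**mITT trigger of 10%.** Let d be the number in mITT but not in the evaluable set.
- One initial group, d = 1: 1/15 = 6.7% on mITT and 1/14 = 7.1% on evaluable, so not met.
- One initial group, d = 2: 2/15 = 13.3% and 2/13 = 15.4%, so met. The same two losses pooled give 2/165 = 1.2%, not met.
- One expanded group, d = 11: 11/120 = 9.2% on mITT, not met; 11/109 = 10.1% on evaluable, met.

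Level and denominator can therefore each change the answer. Protocol 10.10.4.1 also lets the sponsor halt blood collection, or leave samples unanalyzed, in an initial group not selected for expansion. If no 4-week result exists in such a group, the difference is 15/15 = 100% on mITT, while the evaluable denominator is zero and the ratio is undefined.

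**The case against.** SAP 4 and protocol 9.2 agree with each other, and deleting the postviolation words from SAP 6.2 would also remove the conflict. That is fair: the documents do not dictate which side should give way. The time-bounded version is preferable because it keeps valid samples and fits the direction of SAP 3.4.3 and protocol 6.8.1. The protocol already uses a time limit of this kind for Substudy A.

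A reader might infer more than the documents support:
- *That the SAP 6.2 and 2.2.2 clauses are wholly idle.* They are not. The discontinuation and out-of-window parts still act.
- *That an unblinded adjudicator picks the rule case by case.* Sponsor staff are unblinded throughout Substudy B (protocol 10.10.6.2.3). But SAP 4 requires classification before any unblinded analysis, documented under standard procedures, and SAP 6.5.2.2 requires reasons for exclusion to be summarized. Nothing shows that allocation drives the judgment.
- *That the titers are lost to the study.* They leave the evaluable analysis only; the mITT set has no violation criterion.
- *That Group 9 receives the same strains as qIRV.* This cannot be verified. The strains are redacted, final selection is left to the IP manual, and qIRV strains can vary with the time of enrollment.
- *That Group 9 has no composite anywhere.* The tertiary estimands are redacted, so only the secondary estimand can be judged.
- *That the mITT back-up has no threshold.* The 10% figure is stated.

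On the all-strains limit, protocol 10.10.9.1.1 refers back to 10.10.3 for the estimands, so the silence of 10.10.9.3.3 is not a contradiction. The point there is a gap in scope. On mITT, SAP 5.2 already presents summaries by vaccine group and analyzes the enrollment stages separately, so a per-group reading is the natural one.

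**Conclusion.** The conflict between SAP 4 and SAP 6.2 stands. Its size is 3 of 4 or 4 of 5 valid HAI samples dropped from the evaluable analysis for each participant whose only major violation falls between the 4-week and 8-week draws. This assumes that SAP 4 is read literally and that the event is judged major. With no violation rate in the documents, the total cannot be given.

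The all-strains limit leaves out exactly one of 14 groups, with 15 participants in initial enrollment. That is a narrow omission, correctable for the strains that Group 9's own vaccines target.

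The mITT wording and the incomplete window reference are clarifications only.

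All of this is secondary and descriptive. There are no hypotheses, and no error rate or decision rule is affected. The changes are worth making because the tables' Ns should follow from one rule and the cost is small.

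**What to change.** 1. **Violators, Substudy B only.** Reword the SAP 4 bullet to: *no major protocol violation before the 4-week blood draw that follows the last vaccination*. State that a later violation censors only the samples taken after it, as in SAP 6.2. A violation at or before vaccination, or before the 4-week draw, still excludes the participant, so the 4-week requirement keeps its meaning. Samples drawn before a violation that falls between Visits 205 and 206 therefore stay excluded. Show N by time point. Add a matching Substudy B sentence to protocol 9.2 and leave Substudy A unchanged.
2. **All strains.** In protocol 1.1 and 10.10.3, and SAP 2.2, 2.2.2.2.1 and 6.2.2.1, define the population as participants whose assigned schedule targets 2 A and 2 B strains, in one or more injections. Report Group 9's composite for the strains that its vaccines target, without describing them as identical to those in qIRV.
3. **mITT.** Use the SAP 4 rule (*will*, at least 10%) in SAP 5 too, applied per vaccine group within enrollment stage with mITT as denominator. List the Day 21, 1-week and 8-week assay windows in SAP 4.

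**Cost.** Wording, plus the exclusion summaries and listings in SAP 6.5.2.2. SAP 2 lets the SAP modify the protocol plan and ties only major primary-endpoint changes to an amendment. The SAP can therefore be changed first and logged in SAP 2.1, with the protocol aligned at its next amendment. No new samples or assays are needed. The downside is that the 8-week N can be smaller than the 4-week N.
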